## **16. INFORMED CONSENT, ETHICAL REVIEW, AND REGULATORY CONSIDERATIONS**

### **16.1. Informed Consent**

The Principal Investigator or designee is responsible for explaining verbally and in writing the nature, duration, and purpose of the study and possible consequences for treatment. In addition, the Principal Investigator or designee must ensure that the patient understands the potential risks and benefits of participating in the study, including answering any questions the patient may have throughout the study and sharing in a timely manner any new information that may be relevant to the patient's willingness to continue his or her participation in the trial. Patients must also be informed that they may withdraw from the study at any time and for any reason without jeopardizing their future treatment. In accordance with federal regulations (21 CFR 50), all patients enrolled in the study must sign the IRB-approved consent form.

The informed consent document (ICD) will be used to explain the potential risks and benefits of study participation to the patient in simple terms before the patient is entered into the study, and to document that the patient is satisfied with his or her understanding of the risks and benefits of participating in the study and desires to participate in the study.

The investigator is responsible for ensuring that informed consent is given by each patient or legal representative. This includes obtaining the appropriate signatures and dates on the ICD prior to the performance of any protocol procedures and prior to the administration of study drug.

### **16.2. Document Review**

In accordance with federal regulations (21 CFR 312.66), an Institutional Review Board (IRB) that complies with regulations in 21 CFR 56 must review and approve this protocol and the informed consent form prior to initiation of the study. Documentation of IRB approval of the protocol and the ICD must be provided to AROG.

Prior to IRB submission and review, AROG must review and approve all ICDs. All informed consent documents must be compliant with the International Conference on Harmonization (ICH) guideline on good clinical practice (GCP). Informed consent obtained under special circumstances may occur only if allowed by local laws and regulations and performed in accordance with a written process approved by AROG.

Any member of the IRB who is directly affiliated with this study as an investigator or as site personnel must abstain from the IRB's vote on the approval of the protocol.

As well as documentation required by the study site's IRB(s), the following will be provided:

- Current Study Protocol
- The current Investigator's Brochure or package labeling and updates during the course of the study
- Informed consent document

### **16.3. Confidentiality**

Patient medical information obtained for the purposes of this study is confidential, and disclosure to third parties, other than those noted above, is prohibited. Upon the patient's request and written permission, medical information may be given to his/her personal physician or other appropriate medical personnel responsible for the patient's welfare. Data generated for this study must be

available for inspection on request to representatives of the national or local health authorities, and the associated IRB/IEC. Release of research results or data that reveal patient names or other identifiers, such as photographs, audio or videotapes, must be carried out in accordance with Department of Health and Human Services Final Standards for Privacy of Individual Health Information, 45 CFR 164.508. Written authorization must be obtained from the patient and IRB/IEC prior to the release of such information. Identifiable patient data may not be used for purposes of promoting any drugs used in this trial.

#### **16.4. Investigator Information**

Physicians with a specialty in oncology will participate as investigators in this clinical trial.

#### **16.5. Protocol Signatures**

After reading the protocol, each principal investigator will sign the protocol signature page and send a copy of the signed page to an AROG representative.

#### **16.6. Final Report Signature**

The clinical study report coordinating investigator, which may be the Principal Investigator, will sign the final clinical study report for this study, indicating agreement that, to the best of his or her knowledge, the report accurately describes the conduct and results of the study.

The sponsor's responsible medical officer will sign the final clinical study report for this study, confirming that, to the best of his or her knowledge, the report accurately describes the conduct and results of the study. The final clinical study report will be written by the sponsor.

#### **16.7. Publication Statement**

The results of this clinical trial may be used for public dissemination in the form of papers, abstracts, posters, or other informational materials to be presented at scientific meetings, or published in professional journals, or as a part of an academic thesis by an investigator.

Identifiable patient data may not be used for any of these presentations, manuscripts, or reports unless directed by law.

### Appendix I. Inclusion/Exclusion Criteria Checklist

**All subjects enrolled must meet eligibility criteria based on the inclusion/exclusion criteria detailed in the application and approved by the IRB.**

#### **I. Study Information**

Protocol Title:	A Study of Crenolanib and Chemotherapy with Cytarabine and Anthracyclines in Patients with Newly Diagnosed Acute Myeloid Leukemia with FLT3 Activating Mutations
Protocol Number:	ARO-006

#### **II. Subject Information:**

Subject Name/ID:
Gender:  Male  Female

#### **III. Inclusion/Exclusion Criteria**

Inclusion Criteria (From IRB approved protocol)	Yes	No	N/A	Supporting Documentation*
1. Unequivocal diagnosis of AML based on the WHO classification, excluding acute promyelocytic leukemia.				
2. No prior therapy for AML, except for hydroxyurea and/or leukapheresis, in this setting is allowed.				
3. Subjects with AML evolving from MDS with or without prior MDS therapy with demethylating agents will be allowed in the safety phase only .				
4. Subjects must have tested positive for FLT3-ITD and/or other FLT3 activating mutations.				
5. Age $\geq 18$ years will be allowed in the safety phase ; during the expansion phase , subjects must be $\geq 18 - \leq 70$ years of age.				
6. ECOG PS 0 – 2				
7. Adequate liver function, defined as normal bilirubin, ALT $\leq 2.0 \times$ ULN, and AST $\leq 2.0 \times$ ULN measured within 24 hours prior to the induction chemotherapy.				
8. Adequate renal function, defined as serum creatinine $\leq 1.5 \times$ ULN or GFR $> 50$ mL/min				

9. Negative pregnancy test (serum or urine) for women of childbearing potential (WOCBP). 
 
• Women considered not of childbearing potential include any of the following: no menses for at least 2 years or menses within 2 years but amenorrheic for at least 2 months and luteinizing hormone (LH) and follicular stimulating hormone (FSH) values within normal range (according to definition of postmenopausal for laboratory used) or bilateral oophorectomy or radiation castration and amenorrheic for at least 3 months or with bilateral tubal ligation.
 
				
10. WOCBP must practice contraception. Acceptable methods of contraception are double barrier methods (condoms with spermicidal jelly or foam and diaphragm with spermicidal jelly or foam), oral, depo provera, or injectable contraceptives, intrauterine devices, tubal ligations, and abstention.				
11. Male patients (except those with prior surgical contraceptive procedures) with female partners who are of childbearing potential: Recommendation is for male and partner to use effective contraceptive methods, such as latex condoms, during the study.				
12. Able and willing to provide written informed consent.				
Exclusion Criteria (From IRB approved protocol)	Yes	No	N/A	Supporting Documentation*
1. Pre-existing liver diseases (i.e., cirrhosis, chronic hepatitis B or C, nonalcoholic steatohepatitis, and sclerosing cholangitis, etc.)				
2. Known active CNS leukemia				
3. During the expansion phase subjects with therapy-related AML, AML with prior history of MDS with or without prior HMA therapy or AML in the setting of antecedent hematologic disorder.				
4. Subject with concurrent severe and/or uncontrolled medical conditions that in the opinion of the investigator may impair the participation in the study or the evaluation of safety and/or efficacy.				

5. NYHA Class III-IV heart failure, myocardial infarction <6 months prior to study entry and/or serious arrhythmia requiring anti-arrhythmic therapy				
6. Major surgical procedures within 14 days of enrollment (Does not include line placement as needed for chemotherapy administration)				
7. Unwillingness or inability to comply with protocol.				
8. Concurrent use of other investigational agents.				
9. Subjects who are not eligible for standard chemotherapy.				

\*All subject files must include supporting documentation to confirm subject eligibility. The method of confirmation can include, but is not limited to, laboratory test results, radiology test results, subject self-report, and medical record review.

#### **IV. Statement of Eligibility**

This subject is [x eligible / x ineligible] for participation in the study.

Signature: \_\_\_\_\_

Date: \_\_\_\_\_

Printed Name: \_\_\_\_\_

**Appendix II. ECOG Performance Status Criteria**

Performance Status Criteria	
ECOG (Zubrod)	
0	Fully active, able to carry on all pre-disease performance without restriction
1	Restricted in physically strenuous activity, but ambulatory, and able to carry out work of a light or sedentary nature, e.g., light housework, office work
2	Ambulatory and capable of self-care, but unable to carry out any work activities, up and about more than 50% of waking hours
3	Capable of only limited self-care, confined to bed or chair for more than 50% of waking hours
4	Completely disabled; cannot carry on any self care; totally confined to bed or chair

**Appendix III. Patient Diaries: Crenolanib**Cycle No: \_\_\_\_\_ **This section to be completed by Site Study Staff ONLY**

Investigational Drug: Crenolanib  
 Besylate (AR-868,596-26)  
**Protocol ID: ARO-006**

Prescribed Dose: \_\_\_\_\_ mg TID, Dosing: \_\_\_\_\_ 100 mg tablets \_\_\_\_\_ 20 mg tablets

SUBJECT ID

SUBJECT INITIAL

Day	Date m / d / y	Time Taken (HR- MIN AM/PM)	Number of Tablets Taken (100 mg Tablet)	Number of Tablets Taken (20 mg Tablet)	If Dose Skipped Please Provide the Reason/s	With Food	If Yes, please provide Description of Meal	Any Side Effects (Please Complete Adverse Events Form in Detail)
1		/ AM/PM				/ YES/NO		
		/ AM/PM				/ YES/NO		
		/ AM/PM				/ YES/NO		
2		/ AM/PM				/ YES/NO		
		/ AM/PM				/ YES/NO		
		/ AM/PM				/ YES/NO		
3		/ AM/PM				/ YES/NO		
		/ AM/PM				/ YES/NO		
		/ AM/PM				/ YES/NO		
4		/ AM/PM				/ YES/NO		
		/ AM/PM				/ YES/NO		
		/ AM/PM				/ YES/NO		
5		/ AM/PM				/ YES/NO		
		/ AM/PM				/ YES/NO		
		/ AM/PM				/ YES/NO		
6		/ AM/PM				/ YES/NO		
		/ AM/PM				/ YES/NO		
		/ AM/PM				/ YES/NO		
7		/ AM/PM				/ YES/NO		
		/ AM/PM				/ YES/NO		
		/ AM/PM				/ YES/NO		

Cycle No: \_\_\_\_\_ **This section to be completed by Site Study Staff ONLY**

Investigational Drug: Crenolanib  
 Besylate (AR-868,596-26)  
**Protocol ID: ARO-006**

Prescribed Dose: \_\_\_\_\_ mg TID, Dosing: \_\_\_\_\_ 100 mg tablets \_\_\_\_\_ 20 mg tablets

SUBJECT ID

SUBJECT INITIAL

--	--	--	--	--	--	--	--

Day	Date m / d / y	Time Taken (HR- MIN AM/PM)	Number of Tablets Taken (100 mg Tablet)	Number of Tablets Taken (20 mg Tablet)	If Dose Skipped Please Provide the Reason/s	With Food	If Yes, please provide Description of Meal	Any Side Effects (Please Complete Adverse Events Form in Detail)
8		/ / AM/PM				/ / YES/NO		
		/ / AM/PM				/ / YES/NO		
		/ / AM/PM				/ / YES/NO		
9		/ / AM/PM				/ / YES/NO		
		/ / AM/PM				/ / YES/NO		
		/ / AM/PM				/ / YES/NO		
10		/ / AM/PM				/ / YES/NO		
		/ / AM/PM				/ / YES/NO		
		/ / AM/PM				/ / YES/NO		
11		/ / AM/PM				/ / YES/NO		
		/ / AM/PM				/ / YES/NO		
		/ / AM/PM				/ / YES/NO		
12		/ / AM/PM				/ / YES/NO		
		/ / AM/PM				/ / YES/NO		
		/ / AM/PM				/ / YES/NO		
13		/ / AM/PM				/ / YES/NO		
		/ / AM/PM				/ / YES/NO		
		/ / AM/PM				/ / YES/NO		
14		/ / AM/PM				/ / YES/NO		
		/ / AM/PM				/ / YES/NO		
		/ / AM/PM				/ / YES/NO		

Cycle No: \_\_\_\_\_ **This section to be completed by Site Study Staff ONLY**

Investigational Drug: Crenolanib  
 Besylate (AR-868,596-26)  
**Protocol ID: ARO-006**

Prescribed Dose: \_\_\_\_\_ mg TID, Dosing: \_\_\_\_\_ 100 mg tablets \_\_\_\_\_ 20 mg tablets

SUBJECT ID

SUBJECT INITIAL

--	--	--	--	--	--	--

Day	Date m / d / y	Time Taken (HR- MIN AM/PM)	Number of Tablets Taken (100 mg Tablet)	Number of Tablets Taken (20 mg Tablet)	If Dose Skipped Please Provide the Reason/s	With Food	If Yes, please provide Description of Meal	Any Side Effects (Please Complete Adverse Events Form in Detail)
15		/ / AM/PM				/ / YES/NO		
		/ / AM/PM				/ / YES/NO		
		/ / AM/PM				/ / YES/NO		
16		/ / AM/PM				/ / YES/NO		
		/ / AM/PM				/ / YES/NO		
		/ / AM/PM				/ / YES/NO		
17		/ / AM/PM				/ / YES/NO		
		/ / AM/PM				/ / YES/NO		
		/ / AM/PM				/ / YES/NO		
18		/ / AM/PM				/ / YES/NO		
		/ / AM/PM				/ / YES/NO		
		/ / AM/PM				/ / YES/NO		
19		/ / AM/PM				/ / YES/NO		
		/ / AM/PM				/ / YES/NO		
		/ / AM/PM				/ / YES/NO		
20		/ / AM/PM				/ / YES/NO		
		/ / AM/PM				/ / YES/NO		
		/ / AM/PM				/ / YES/NO		
21		/ / AM/PM				/ / YES/NO		
		/ / AM/PM				/ / YES/NO		
		/ / AM/PM				/ / YES/NO		

Cycle No: \_\_\_\_\_ **This section to be completed by Site Study Staff ONLY**

Investigational Drug: Crenolanib  
 Besylate (AR-868,596-26)  
**Protocol ID: ARO-006**

Prescribed Dose: \_\_\_\_\_ mg TID, Dosing: \_\_\_\_\_ 100 mg tablets \_\_\_\_\_ 20 mg tablets

SUBJECT ID

SUBJECT INITIAL

--	--	--	--	--	--	--

Day	Date m / d / y	Time Taken (HR- MIN AM/PM)	Number of Tablets Taken (100 mg Tablet)	Number of Tablets Taken (20 mg Tablet)	If Dose Skipped Please Provide the Reason/s	With Food	If Yes, please provide Description of Meal	Any Side Effects (Please Complete Adverse Events Form in Detail)
22		/ / AM/PM				/ / YES/NO		
		/ / AM/PM				/ / YES/NO		
		/ / AM/PM				/ / YES/NO		
23		/ / AM/PM				/ / YES/NO		
		/ / AM/PM				/ / YES/NO		
		/ / AM/PM				/ / YES/NO		
24		/ / AM/PM				/ / YES/NO		
		/ / AM/PM				/ / YES/NO		
		/ / AM/PM				/ / YES/NO		
25		/ / AM/PM				/ / YES/NO		
		/ / AM/PM				/ / YES/NO		
		/ / AM/PM				/ / YES/NO		
26		/ / AM/PM				/ / YES/NO		
		/ / AM/PM				/ / YES/NO		
		/ / AM/PM				/ / YES/NO		
27		/ / AM/PM				/ / YES/NO		
		/ / AM/PM				/ / YES/NO		
		/ / AM/PM				/ / YES/NO		
28		/ / AM/PM				/ / YES/NO		
		/ / AM/PM				/ / YES/NO		
		/ / AM/PM				/ / YES/NO		

Cycle No: \_\_\_\_\_ **This section to be completed by Site Study Staff ONLY**

Investigational Drug: Crenolanib  
Besylate (AR-868,596-26)  
**Protocol ID: ARO-006**

Prescribed Dose: \_\_\_\_\_ mgTID, Dosing: \_\_\_\_\_ 100 mg tablets \_\_\_\_\_ 20 mg tablets

SUBJECT ID

SUBJECT INITIAL

--	--	--	--	--	--	--	--

Day	Date m / d / y	Time Taken (HR- MIN AM/PM)	Number of Tablets Taken (100 mg Tablet)	Number of Tablets Taken (20 mg Tablet)	If Dose Skipped Please Provide the Reason/s	With Food	If Yes, please provide Description of Meal	Any Side Effects (Please Complete Adverse Events Form in Detail)
		/ / AM/PM				/ / YES/NO		
		/ / AM/PM				/ / YES/NO		
		/ / AM/PM				/ / YES/NO		
		/ / AM/PM				/ / YES/NO		
		/ / AM/PM				/ / YES/NO		
		/ / AM/PM				/ / YES/NO		
		/ / AM/PM				/ / YES/NO		
		/ / AM/PM				/ / YES/NO		
		/ / AM/PM				/ / YES/NO		
		/ / AM/PM				/ / YES/NO		
		/ / AM/PM				/ / YES/NO		
		/ / AM/PM				/ / YES/NO		
		/ / AM/PM				/ / YES/NO		
		/ / AM/PM				/ / YES/NO		
		/ / AM/PM				/ / YES/NO		
		/ / AM/PM				/ / YES/NO		
		/ / AM/PM				/ / YES/NO		
		/ / AM/PM				/ / YES/NO		
		/ / AM/PM				/ / YES/NO		
		/ / AM/PM				/ / YES/NO		
		/ / AM/PM				/ / YES/NO		

## Appendix IV. Study Schedule

### I. Induction

Assessment	Screening a	Baseline	On Treatment - Induction 1 and 2			
Day	-28 days of enrollment, unless otherwise specified	First day of crenolanib	Weekly following start of crenolanib	Day 14-28 (response assessment visit)	Day 42 ± (3 days) or at count recovery + (whichever is first)	Weekly until end of cycle (if cycle is extended past 42 days)
Demographics	X					
Relevant medical history, current medical conditions including AML-specific history	X					
Evaluation of FLT3 and other mutational status	X				X	
Prior/Concomitant medications and significant non-drug therapies	X	X	Per SOC	X	X	Per SOC
Physical examination with ECOG PS	X	X	Per SOC	X	X	Per SOC
EKG b		X**				
Vitals, Weight, and Height (only at screening)	X	X	Per SOC	X	X	Per SOC
Assessment of adverse events, toxicities		X	Per SOC	X	X	Per SOC
Hematology (CBC with differential)	X*	X	X d	X	X	X d
Serum Chemistries (CMP with bilirubin, ALT/AST and creatinine)	X*	X	X d	X	X	X d
Urine or serum pregnancy test	X		Every 6 months while patient is on study			
Blood collections for PK and correlative sciences c			X** (drawn per Section 11)			
Bone marrow biopsy and aspirate	X*			X e	X	

**Key:**

a count recovery is defined as : ANC  $\geq$ 1000 and platelets  $\geq$ 100,000

a Screening assessments should be performed within 28 days of enrollment with the following exceptions: CBC, CMP and pregnancy test (when applicable) should be performed within 7 days of enrollment, bone marrow biopsy and aspirate and evaluation of FLT3 and other mutational status should be performed within 21 days of enrollment

\* If screening assessments were performed while patient was receiving induction chemotherapy, the following assessments performed prior to starting induction, if done per standard of care, may be requested by the sponsor: CBC with differential, CMP with bilirubin, ALT/AST, and bone marrow biopsy and aspiration

b EKG is to be performed pre-dose crenolanib (baseline on the first day of crenolanib) as well as 2 hours ( $\pm$  30 minutes) post first dose of crenolanib during Induction 1

c Peripheral and whole blood samples for translation research (including PK analysis) should be collected as defined in Section 11.

\*\* EKG, Peripheral blood for PK analysis and Whole blood sample will only be collected during Induction 1

d CBC with differential and CMP should be performed at least weekly while patients are receiving crenolanib during induction. Additional labs may be performed per SOC, for safety, the sponsor may request additional labs done per SOC be captured

e Bone marrow biopsy and aspirate performed on day 14-28 should have FLT3 testing and mutational status if available

Per SOC: Physician visits (with ECOG PS, vitals, weight, concomitant medication assessment and adverse events assessments) should be performed as per SOC while patients are receiving crenolanib during induction. At a minimum adverse events and concomitant medications should be reported to the sponsor (per EDC) monthly.

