**13.2. Safety monitoring during the initial safety phase**

Adverse events, as defined in Section 14.1, will be monitored during the treatment and post-treatment follow up periods. Adverse events will be monitored on a continuous basis by the sponsor.

The Protocol Safety Committee will review safety data from this trial on a periodic basis. The committee also will monitor the safety outcomes listed below for purposes of determining if enrollment in one or both cohorts should continue or be halted. Within each cohort, up to 6 patients will be initially enrolled. For the first 6 patients, patients will be enrolled in a sequential manner such that no more than 3 patients are within 30 days of starting induction 1 therapy. Enrollment will be halted within a cohort if an apparent increase is observed in the occurrence of one or more of the following outcomes:

- Early mortality due to any cause
- Expected, non-hematologic, crenolanib-related toxicity (CTCAE Grade 4)
- Unexpected, non-hematologic, crenolanib-related toxicity (CTCAE Grade 4)

The criteria used to determine if enrollment will be halted are described in sections 13.2.1, 13.2.2 and 13.3.3.

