### **13.2.2. Excessive expected crenolanib-related toxicity**

Early stopping rules for excessive expected crenolanib-related toxicity will be applied in the safety phase of the study. In clinical studies of crenolanib as single-agent therapy, the following treatment-related, non-hematologic, adverse events were the most frequently reported, irrespective of severity:

- hepatic dysfunction
- nausea, vomiting, and diarrhea
- ascites, edema, and effusions

The majority of these events were CTCAE severity grade 1-3, with grade 4 representing less than 5% of total cases reported. It's anticipated that these or similar adverse events also occur with relatively higher frequency for AML induction regimens that include cytarabine, idarubicin, or daunorubicin. Nonetheless, for purposes of monitoring enrollment in this study, the adverse events listed above represent the expected non-hematologic crenolanib-related toxicities. If the observed rate of expected, non-hematologic, crenolanib-related toxicity with CTCAE severity grade 4 exceeds 20% during the first 60 days of treatment, then enrollment will be halted as follows:

If 2 or more of the first 6 patients enrolled within a cohort experience a CTCAE grade 4, non-hematologic, expected crenolanib-related adverse event prior to Day 60 then enrollment of additional patients within that cohort will be halted pending review by the Protocol Safety Committee. Otherwise, 6 additional patients will be enrolled within the cohort provided none of the other stopping criteria have been met. Upon enrollment of the 6 additional patients within a cohort, if 3 or more of the patients enrolled within a cohort experience such an event prior to Day 60, then enrollment of additional patients will be halted pending review by the Protocol Safety Committee. If these and the other early stopping criteria are not met, then 12 additional patients will be enrolled to the cohort.

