#### **14.4. Adverse Event Reporting**

AROG has standards for reporting AEs that are to be followed regardless of applicable regulatory requirements that may be less stringent. Lack of drug effect is not an AE in clinical trials, because the purpose of the clinical trial is to establish drug effect.

Adverse Events (AEs) will be evaluated according to CTCAE version 4.03 and documented in medical record. After the Informed Consent Document (ICD) is signed, study site personnel will record the occurrence and nature of each patient's pre-existing conditions, including clinically significant signs and symptoms of the disease. During the study, site personnel will record any change in the pre-existing condition(s) and the occurrence and nature of any new adverse events.

All AEs related to protocol procedures are reported to AROG or designee. All AEs occurring after the patient receives the first dose of study drug must be reported to AROG or its designee via CRF. Investigators will be instructed to report to AROG or its designee their assessment of the potential relatedness of each AE to protocol procedure, studied disease state, study drug, and/or drug delivery system via CRF.

For all AEs, the investigator should specify:

1. ***Seriousness:*** Seriousness of an AE is defined by the criteria described in Section 10.1. A severe AE should not always be considered as serious.
2. ***Date of onset and its duration (start and end dates):*** The investigator should follow up the outcome of any AEs until they return to normal or consolidation of the subject's condition. All adverse events still evolving at the end of the study are to be followed up by the investigator until their resolution or stabilization.
3. ***Severity:*** (using NCI CTCAE v.4.03),

4. **Action taken with respect to study drug:** (no action taken; study drug dosage adjusted/temporarily interrupted; study drug permanently discontinued due to this adverse event; hospitalization/prolonged hospitalization), corrective treatment/therapy given, additional investigations performed
5. **Outcome:** Resolved/Recovered, recovering/resolving, not recovered/resolved, recovered/resolved with sequelae, unknown
6. **Relatedness:** If an AE is related or not related to study drug

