### **14.5. Serious Adverse Event Reporting**

Serious adverse event collection begins after the patient has signed informed consent and has received a tablet or more of study drug. If a patient experiences an SAE after signing informed consent, but prior to receiving study drug, the event will NOT be collected unless the investigator feels the event may have been caused by a protocol procedure.

In case of a SAE, the investigator, within 24 hours of learning of the SAE or subject death, must notify the sponsor (Arog Pharmaceuticals by e-mail: [contact] or [contact]) and transmit the following information (within a signed SAE report form):

- Subject identification code, demographics and vitals
- Description of event with onset and duration (with CTCAE event term & severity)
- Dates, dose and frequency of study drug administered
- Assessment of the seriousness and causality of the event with the study drug using the causality criteria (EVCTM): related versus not related
- Study drug status (dose interrupted or discontinued)
- Date of death (if applicable)
- Concomitant therapy and interventions
- Pertinent laboratory data/diagnostic tests
- Pertinent medical history including underlying diagnosis

All SAEs must be followed by the investigator until resolution or stabilization until the subject's death. This may mean that follow-up will be extended beyond the subject's withdrawal from the trial. The investigator must provide follow-up information (outcome, more precise medical details, results of investigations, copy of discharge summary, etc...) within 24 hours of information becoming available to Arog Pharmaceuticals and to the study monitor, again using the SAE Report Form indicating follow-up. When this information is passed on, care must be taken to continue to respect subject anonymity. The study monitor may contact, or visit the investigator, in order to obtain details of the event.

The sponsor will report all SUSAR to the country specific regulatory authorities within the request period. The evaluation of expectedness is based on knowledge of the adverse reaction on the reference document: the current reference document is the latest version of the Investigator's Brochure of crenolanib.

The sponsor will also inform the IRB of any SAE with the potential to modify the benefit/risk ratio of the present study. The sponsor will be responsible for reporting of New Safety Issues and Annual Safety Reports to IRBs.

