#### **14.6. Follow-up of Adverse Events**

All adverse events will be followed up according to Good Clinical Practice.

**During Treatment:** During study, site personnel will track any change in the condition(s) and the occurrence and nature of any AEs and record the highest grade of the adverse event per cycle on the CRF. CTCAE grading will be assigned before each visit for any adverse events experienced during the previous visit period.

**Preparation for transplant:** Once patient enters conditioning prior to transplant, crenolanib will be held (72 hours prior to start of conditioning). Patients will not be followed for safety once conditioning starts. If patient receives maintenance crenolanib following transplant, safety will be assessed once patient restarts crenolanib (per protocol).

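### Non-serious Grade 4 events count toward two of the three safety-phase halting rules but have no expedited report, so a cohort can keep enrolling for a time after meeting its trigger

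*Combined protocol and SAP*

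**What the plan says.** **Halting rules.** Section 13.2.2 halts a cohort for expected toxicity: "If 2 or more of the first 6 patients enrolled within a cohort experience a CTCAE grade 4" event of the listed kind before Day 60, or 3 or more once 12 are enrolled. Section 13.2.3 does the same for unexpected toxicity at 1 of the first 6 or 2 of 12. The third rule (13.2.1) counts deaths.

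**Reporting routes.**
- SAEs and deaths (14.5): the investigator, "within 24 hours of learning of the SAE or subject death, must notify the sponsor".
- All other events (14.4): "All AEs occurring after the patient receives the first dose of study drug must be reported to AROG or its designee via CRF". No time limit is given.
- CRF grading (14.6): sites "record the highest grade of the adverse event per cycle on the CRF". An induction cycle may last longer than 28 days (8.3).
- Minimum frequency (Appendix IV, Induction key, repeated in the Consolidation key): "At a minimum adverse events and concomitant medications should be reported to the sponsor (per EDC) monthly".

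**Grade and seriousness.** None of the criteria in 14.1.2 refers to CTCAE grade, and 14.4 adds: "A severe AE should not always be considered as serious".

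**Oversight.** Section 13.2 states: "Adverse events will be monitored on a continuous basis by the sponsor". Section 15.2 plans site calls about twice a month, and data safety meetings at least every six months or for every 6 patients enrolled per cohort.

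**The concern.** A rule that acts on one, two or three patients protects the next patients only if the sponsor knows the count before they start. The trial is multi-center (8.2). If the events fall at different sites, only the sponsor can add them up. As written, a non-serious Grade 4 event can wait for the monthly data entry with every site fully compliant, and the cohort goes on enrolling although its trigger has been met.

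**Working it through.** **1. The plan's own counts.** The trigger is the smallest r with r/n above the stated rate.
- Expected, 20%: 6 × 0.20 = 1.2, so r = 2 (33.3%); 12 × 0.20 = 2.4, so r = 3 (25.0%).
- Unexpected, 15%: 6 × 0.15 = 0.9, so r = 1 (16.7%); 12 × 0.15 = 1.8, so r = 2 (16.7%).

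All four match 13.2.2 and 13.2.3. The counts are sound; the question is when the sponsor learns of the events.

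**2. Which Grade 4 events can miss the 24-hour clock.** In Appendix V, Grade 4 anorexia, diarrhea, vomiting, pleural effusion and pericardial effusion are all worded as life-threatening, so they would ordinarily be SAEs under 14.1.2. ALT and AST (above 20x ULN) and bilirubin (above 10x ULN) are graded on the laboratory value alone. Such a value would be recorded as an adverse event, because Tables 6 and 7 interrupt crenolanib from Grade 2 and 14.4 records laboratory findings that change dosing. It need not be an SAE if there is no admission, prolonged stay or other criterion in 14.1.2. Hepatic dysfunction is on the expected list in 13.2.2, so the relevant trigger is 2 of 6 or 3 of 12.

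**3. Worst case within the first 6.** The stagger in 13.2 allows at most 3 patients within 30 days of starting induction. An illustrative timeline:
- Patients 1 to 3 start on Day 1; crenolanib begins about Day 9 (5.8).
- Two have a non-serious Grade 4 ALT by Day 25, so 2 of 6 is reached.
- Monthly entry may fall as late as about Day 25 + 30 = Day 55.
- Patients 4 to 6 may start from Day 31.

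All 3 could start after an unreported trigger.

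**4. Simple product.** Extra patients = accrual per month × lag / 30. The documents give no accrual rate, so 1 to 3 patients per month per cohort is assumed.
- 30-day lag: 1.0 to 3.0
- 15-day lag (roughly the site-call interval): 0.5 to 1.5
- 1-day lag: 0.03 to 0.1

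**5. Simulation.** The first 12 patients of a cohort were simulated under the expected-toxicity rule. Assumptions: random arrivals, the stagger applied to the first 6, a true Grade 4 rate of 20%, and event times uniform on Days 9 to 60. The documents do not say whether enrollment pauses after patient 6 until Day 60, so both readings were run. Mean patients enrolled after the trigger, given a trigger:

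| Accrual per month | Pause after 6 | 30-day lag | 15-day lag | 1-day lag |
|---|---|---|---|---|
| 1 | yes | 0.585 | 0.295 | 0.020 |
| 1 | no | 0.793 | 0.402 | 0.026 |
| 2 | yes | 0.711 | 0.344 | 0.025 |
| 2 | no | 1.389 | 0.716 | 0.048 |
| 3 | yes | 0.712 | 0.352 | 0.025 |
| 3 | no | 1.703 | 0.963 | 0.067 |

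At a true rate of 30% the ranges are 0.6 to 1.9 (30 days) and 0.3 to 1.0 (15 days). Two limits pull in opposite directions. Grade 4 events already reported as SAEs were not removed, so the figures are high on that account. Patients after the twelfth are not counted, so they are low on that account.

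**The case against.** **Narrow reach.** Most Grade 4 terms in Appendix V are life-threatening by definition, and 14.3 describes Grade 4 that way for terms CTCAE does not define. Those already reach the sponsor within 24 hours. This stands and limits the point mainly to laboratory-defined events. Section 13.2.2 also puts Grade 4 at under 5% of reported cases of these toxicities with single-agent crenolanib. That is a share of cases, not of patients, and it bears on how often a trigger would occur, not on what happens once one does.

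**Stronger readings that the documents do not support.**
- A reader might infer that one asymptomatic ALT above 20x ULN halts a cohort unseen. It does not: 13.2.3 excludes the toxicities listed in 13.2.2, so a single event trips a Grade 4 rule only if it is unexpected.
- A reader might infer that all the halting rules are affected. The mortality rule is not part of this point, since 14.5 gives deaths the 24-hour clock. Section 14.8 routes deaths plainly due to progression differently, which is a separate matter.
- A reader might infer that enrollment after patient 6 is unlimited. The stagger does end there, but 13.2.1 to 13.2.3 set decision points at 6 and 12 patients.

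**Worst-case lag.** Thirty days is a maximum. If events fall evenly within the interval, the mean wait is about 15 days, or about 7 if they are raised at the site calls. This stands for size.

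**Existing controls.** The monthly interval is a floor, the sponsor monitors continuously, and it confirms each enrollment (7.3 and 10), so it could ask about current patients first. Training material (section 15) may also set entry times. But nothing in the documents requires a site to report these events on a call, and continuous monitoring has no deadline behind it. Section 8.5 asks for sponsor discussion before a hold only when the reason is not crenolanib-related toxicity, so a hold for the events the rules count needs no prior contact.

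**Conclusion.** The point holds within limits. No two sections conflict and the halting counts are correct. What is missing is a reporting deadline for non-serious Grade 4 events that two of the three rules depend on, so a fully compliant cohort can meet its trigger and continue enrolling.

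The worst case is a lag of about 30 days with up to 3 of the first 6 patients starting in that time. The average is smaller: about 0.6 to 1.7 patients per triggered cohort at a 30-day lag and 0.3 to 1.0 at 15 days. These averages rest on assumed accrual of 1 to 3 patients per month per cohort, a true Grade 4 rate of 20% and the event timing above. As a rough check on the accrual assumption, if the 2 to 3 years in the synopsis were all accrual, 120 patients would be 120/36 = 3.3 to 120/24 = 5 per month for the whole trial, or 1.7 to 2.5 for each of two cohorts. Accrual would be faster if that period includes follow-up.

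This is a cheap improvement to safety monitoring, not a flaw that undermines the design.

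**What to change.** 1. Add to 13.2 and 14.5: during the safety phase, any non-hematologic Grade 4 event with onset up to Day 60 that is related, possibly related or of unknown relation to crenolanib is reported to the sponsor within 24 hours of awareness, whether or not it is serious.
2. Add to 13.2: the sponsor checks the counts in 13.2.1 to 13.2.3 before issuing any further Confirmation of Enrollment in that cohort.
3. In both Appendix IV keys (Induction and Consolidation), except these events from the monthly minimum.

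Limiting the duty to events not judged unrelated keeps it to those the rules could count. On the simulation above, a 1-day lag brings the mean excess down to 0.02 to 0.07 patients.

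The cost is protocol wording and a few extra expedited reports in about 48 patients. The reporting route and the enrollment confirmation step already exist.
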